5.5. Screening record

Any patient initially considered suitable, but then found inappropriate due to study exclusion criteria will be recorded into the screening record.

6. Clinical events

6.1. Definitions

The following definitions will be employed in this study.

Statin intolerance

Development of an increase in creatine kinase OR AST/ALT elevation > 3x upper limit of normal OR rhabdomyolysis with statin initiation during the study period.

History of statin intolerance

History of an increase in creatine kinase OR AST/ALT elevation > 3x upper limit of normal OR rhabdomyolysis with statin initiation, prior to enrollment in this study

Moderate risk for ASCVD

7.5%-20% 10-year ASCVD risk by the Pooled Cohorts Equation

Severe Mental Illness

History of schizophrenia or another mental illness with psychotic features

6.2 Reporting procedures

Clinical Events Committee

The CEC is made up of cardiologists who are not participants in the trial. The CEC is charged with the development of specific criteria used for the adjudication of clinical events and clinical endpoints in the trial which are based on protocol.

The Clinical Events Committee will establish explicit rules outlining the minimum amount of data required, and the algorithm followed in order to classify a clinical event. All members of the Clinical Events Committee will be blinded to the treatment arm and the primary results of the trial.

The Clinical Events Committee will meet regularly to review and adjudicate all clinical events in which the required minimum data is available. The Committee will also review and rule on all deaths that occur throughout the trial.

Reports of clinical events should be submitted within 15 days of the Chief Investigator becoming aware of the event.

Local investigators should report any clinical events as required by their Local Research Ethics Committee, Sponsor and/or Research & Development Office.

Contact for reporting clinical events: [name]
Email: [contact]

Case report form

An online CRF form will be used throughout the study. This will be secure, and compatible with currently guidelines to ensure security of patient data. It will be managed via the Lithuanian University of Health Sciences Clinical Trials Unit , and data achieved securely.

7. Assessment and follow-up

Routine follow-up will be performed with a clinic visit at 6 months in the control group and at 2 months and 8 months in the intervention group. The CRF should be completed.

8. Statistics and data analysis

Data will be summarised as mean (SD) or median (interquartile range) for skewed data. Statistical comparisons will be undertaken using a paired Student's t-test (after log transformation if necessary) or nonparametric alternative if data are not normalised by log transformation. Kaplan-Meier survival analysis curves will be used to assess clinical event timelines.

9. Regulatory issues

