1.1. Study overview diagram

4.2 Study protocol:

Patients meeting the study criteria will be enrolled at outpatient cardiology clinics at four centers: Lithuanian University of Health Sciences, Northway Medical Centre, Prienu Hospital, and Unomeda Medical Centre. The enrolment period will last six months, with an estimated 50 patients per month enrolled into the study, for a total of 300 patients.

Patients will be randomized to either the control group or the intervention group. Baseline variables will include demographic variables (age, gender, BMI, blood pressure, heart rate), medical history (hypertension, hyperlipidaemia, type 2 diabetes mellitus, tobacco use), laboratory variables (total cholesterol, HDL, LDL, triglycerides, AST, ALT, creatine kinase, and, vitamin D levels) and socioeconomic variables (education level, income level, rural or urban, and marriage status).

The control group will be provided reassurance through a short, semi-structured discussion on the excellent safety profile of statins, similar to a typical interaction between a clinician and patient. They will then be prescribed 30mg atorvastatin daily as a 30 tablets supply with five patient-initiated re-fills for 30 tablets each. Final follow-up in this group will occur at 6 months.

The intervention group will be offered a red yeast rice extract 20mg nightly to achieve a goal LDL-cholesterol of <2.6 mmol/L (100 mg/dL) in accordance with the 2019 ESC/EAS guidelines (9). Initial follow-up will take place in 2 months to assess the efficacy of their treatment. Patients who are not at the goal LDL-cholesterol will be prescribed 30mg atorvastatin nightly as a 30 tablets supply with five patient-initiated re-fills for 30 tablets each, with final follow-up after 6 additional months. Patients who are at goal on the red yeast rice extract will be recommended to switch to lovastatin 20mg nightly as a bio-identical substitute, but they will be excluded from further analysis.

In both groups, statin adherence will be assessed by pharmacy refill records at the final follow-up. A short, four question questionnaire (Appendix A) will be administered at this point as well. Final follow-up laboratory variables collected will include total cholesterol, HDL, LDL, triglycerides, AST, ALT, creatine kinase, and vitamin D levels.

Conversation guidelines for each clinical encounter in the intervention group are included in Appendix B.

Randomisation

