4.3. Study outcome measures

Primary Endpoint

Rate of statin compliance, based on pharmacy refill records. Values per patient can range from 0-6 according to the number of refills.

Secondary Endpoints:

Rate of perceived side-effects from statin use, including muscle aches, fatigue, mental fog, and gastrointestinal upset.

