4.5. Sample size/Power calculation

This study is designed as a superiority trial. Based on prior literature, we estimate a 50% statin compliance rate with a standard deviation of 10% (2). We will set the minimal detectable effect at a 5% increase in statin compliance, with an $\alpha < 0.05$ and power of 0.9. Based on case-to-control ratio of 1:1, our total minimum sample size for the primary endpoint is 138. However, we will plan on a total sample size of 300 patients, to account for patients who drop out of the study as well as patients who will be excluded due to attaining an LDL-cholesterol of <2.6 mmol/L (100 mg/dL) on red yeast rice extract.

5. Participant entry

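### Section 8 prescribes a paired t-test, but the primary endpoint compares two independent, unmatched arms

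*Protocol*

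**What the plan says.** Section 8 of the protocol gives one rule for all comparisons: "Statistical comparisons will be undertaken using a paired Student's t-test (after log transformation if necessary) or nonparametric alternative if data are not normalised" by the transformation. The only other technique it names is descriptive and concerns something else: "Kaplan-Meier survival analysis curves will be used to assess clinical event timelines".

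On the design, section 4.2 says "Patients will be randomized to either the control group or the intervention group". The randomisation paragraph alternates whole weeks between arms and matches no individuals.

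On the primary endpoint, section 4.3 says "Rate of statin compliance, based on pharmacy refill records. Values per patient can range from 0-6 according to the number of refills", and section 4.2 fixes the timing: "In both groups, statin adherence will be assessed by pharmacy refill records at the final follow-up".

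On who is analysed, section 4.2 says of intervention patients who reach the LDL goal on red yeast rice: "but they will be excluded from further analysis".

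On sample size, section 4.5 assumes 50% compliance with an SD of 10%, a 5% increase, alpha 0.05 and power 0.9. It concludes: "Based on case-to-control ratio of 1:1, our total minimum sample size for the primary endpoint is 138".

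**The concern.** A paired test analyses differences within linked pairs: the same patient measured twice, or two patients matched by design. Neither applies to the primary endpoint. Each patient belongs to one arm and contributes one refill count. There is no pre-treatment count to pair it with, because patients must decline statins to enter (section 5.2) and are excluded if already on lipid-lowering therapy (section 5.3).

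That leaves two readings of section 8. Either patients are paired across arms by some rule the protocol does not give, or the test is a within-patient one and does not compare the arms at all. The symptom endpoint, asked once at final follow-up, has no pairs either.

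At stake is whether the primary analysis is defined. An analyst following section 8 literally would have to choose pairs. The p-value would depend on that choice, and every patient without a partner would drop out. Unequal analysed arms are to be expected, because the at-goal exclusion applies to the intervention arm only.

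**Working it through.** **Which calculation gives 138?**

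Inputs from section 4.5: difference δ = 5, SD σ = 10, alpha 0.05 (sidedness not stated), power 0.90 (z = 1.2816), ratio 1:1.

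Two independent means, per arm: n = 2(z_α + z_β)²(σ/δ)².
- One-sided: 2 × (1.6449 + 1.2816)² × 2² = 68.5, so 69 per arm and **138 in total**. This is the stated figure.
- Two-sided: 2 × (1.9600 + 1.2816)² × 2² = 84.06, so 85 per arm and 170 in total.

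Paired means, with the SD of 10 read as the SD of the differences: pairs = (z_α + z_β)²(σ_d/δ)².
- One-sided: 34.3, so 35 pairs (70 patients).
- Two-sided: 42.03, so 43 pairs (86 patients).

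If the SD of 10 is instead the SD of single values, the SD of differences is 10√(2(1 − ρ)). One-sided, the paired formula then returns 69 pairs when ρ = 0 (SD of differences 14.14), which is the independent case again. Section 4.5 is therefore an independent-groups calculation.

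**What would forced pairing cost?**

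The protocol does not say how many intervention patients will be excluded. The arm sizes below are assumptions, with all 150 controls analysed. With k = min(n_c, n_i) pairs:
- variance of the difference, paired relative to unpaired: (2/k) / (1/n_c + 1/n_i);
- power from the noncentral t distribution, standardised difference 5/10 = 0.5, two-sided 0.05.

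| Controls v intervention | Controls discarded | Variance ratio | Power unpaired | Power paired |
|---|---|---|---|---|
| 150 v 150 | 0 | 1.00 | 99.1% | 99.0% |
| 150 v 125 | 25 | 1.09 | 98.4% | 97.5% |
| 150 v 100 | 50 | 1.20 | 97.1% | 93.8% |
| 150 v 75 | 75 | 1.33 | 94.1% | 85.6% |

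Example for 150 v 100: (2/100) / (1/150 + 1/100) = 0.0200/0.01667 = 1.20.

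**How far does the answer depend on the pairing?**

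Simulation with normal data, the unpaired p fixed at 0.03, 200 data sets and 500 random pairings of each:

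| Arms | Pairings with p < 0.05 | Central 95% of p-values (mean limits) |
|---|---|---|
| 150 v 150 | 99.6% | 0.019 to 0.045 |
| 150 v 100 | 51% | 0.005 to 0.23 |
| 150 v 75 | 42% | 0.004 to 0.36 |

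The simulated type I error of arbitrary pairing is 0.051 (150 v 100) and 0.050 (150 v 75), so the test remains valid in that narrow sense.

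**Log transformation.** Section 4.3 says "Values per patient can range from 0-6 according to the number of refills". The logarithm of zero is undefined, so the conditional transformation fails for any patient with no fills. This is a caution and not part of the main argument.

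**The case against.** The strongest reply is that the word paired is a drafting slip that would correct itself. Section 8 is brief and generic, and text from another study is visible nearby: section 10.2 speaks of CABG centres and section 9.1 of NHS Trusts. A paired t-test does not run on arms of unequal length, so an analyst would notice and use an independent-samples test. This is plausible. But it is the only comparison method in the protocol, and it is stated wrongly, not left open, so a later analysis plan would have to contradict it.

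The magnitude is hypothetical. The protocol nowhere says strangers will be paired, and the arm sizes are assumed. Dropout and withdrawal for intolerance can also thin the control arm, which would narrow the imbalance. Paired power falls below 90% only when about 65 of the 150 intervention patients (43%) are excluded with no control loss: 85 pairs give 89.7%. The simulation uses normal data and a deliberately borderline p-value. All of this stands as a limit on size, not as a defence of the test.

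The conflict with section 4.5 is inferred, since that section names neither a test nor sidedness and 138 needs a one-sided 0.05. That is fair, but the mismatch with the design in sections 4.2 and 4.3 does not depend on it.

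The nonparametric alternative is not named, so a rank-sum test is not expressly ruled out. That is also true, but offered as the alternative to a paired t-test it reads most naturally as the signed-rank test.

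A paired test might have been intended for laboratory change. Section 8 does not limit it to that; if it did, the primary endpoint would have no stated test.

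**Conclusion.** The concern holds and must be fixed. The primary comparison in section 8 does not fit the design in sections 4.2 and 4.3, and it disagrees with the independent-groups calculation that reproduces the 138 in section 4.5.

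The harm is an undefined primary analysis and, if pairs are forced, a result that depends on an arbitrary choice and wastes data. It is not bias or an inflated false-positive rate. With equal analysed arms the numerical effect is negligible. With the assumed 125, 100 or 75 intervention patients against 150 controls, the variance rises by 9%, 20% or 33%, and only the last case takes power below the planned 90%. These sizes rest on the assumed exclusions, on no loss of controls and on the design values of section 4.5. That the test is the wrong one rests on none of them.

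**What to change.** In section 8, replace the paired t-test with an unpaired between-arm comparison of the number of fills: an independent two-sample t-test with a 95% confidence interval for the difference, the Wilcoxon rank-sum test as the named nonparametric alternative, and no log transformation of the 0–6 count. State that symptom rates are compared between arms as proportions. If paired tests are kept, confine them to within-patient laboratory change from baseline to final follow-up.

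State whether the test is one- or two-sided. The 138 corresponds to one-sided 0.05; a two-sided test needs 170, which the planned 300 also exceeds, with a margin of 130 for dropout and exclusions.

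The cost is one or two sentences, with no new data, patients or sample size. The week-by-week allocation is a separate matter that this change does not resolve; if it is addressed, the replacement test may need to reflect it.

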9.1. Ethics approval

The Chief Investigator will obtain approval from the TBC Research Ethics Committee. The study must be submitted for Site Specific Assessment (SSA) at each participating NHS Trust. The Chief Investigator will require a copy of the Trust R&D approval letter before accepting participants into the study. The study will be conducted in accordance with the recommendations for physicians involved in research on human subjects adopted by the 18th World Medical Assembly, Helsinki 1964 and later revisions.

9.2. Consent

Consent to enter the study must be sought from each participant only after a full explanation has been given, an information leaflet offered and time allowed for consideration. Signed participant consent should be obtained. The right of the participant to refuse to participate without giving reasons must be respected. After the participant has entered the study the clinician remains free to give alternative treatment to that specified in the protocol at any stage if he/she feels it is in the participant's best interest, but the reasons for doing so should be recorded. In these cases the participants remain within the study for the purposes of follow-up and data analysis. All participants are free to withdraw at any time from the protocol treatment without giving reasons and without prejudicing further treatment.

9.3. Risks of procedure

No procedures are involved in this study

9.4. Confidentiality

The Chief Investigator will preserve the confidentiality of participants taking part in the study and is registered under the Data Protection Act.

9.5. Indemnity

Lithuanian University of Health Sciences holds negligent harm and non-negligent harm insurance policies which apply to this study.

9.6. Sponsor

Lithuanian University of Health Sciences will act as the main Sponsor for this study. Delegated responsibilities will be assigned to the NHS trusts taking part in this study.

9.7. Funding

This study is not funded

9.8. Audits

The study may be subject to inspection and audit by Lithuanian University of Health Sciences under their remit as sponsor and other regulatory bodies to ensure adherence to GCP and the NHS Research Governance Framework for Health and Social Care (2nd edition).

10. Study management

The day-to-day management of the study will be co-ordinated through **Lithuanian University of Health Sciences**.

10.1. Study reporting

We anticipate that it will take 6 months to complete patient recruitment and another 8 months to complete follow-up. We will aim to begin recruitment after Ethics review approval with first results available for presentation in late 2023

10.2. Study sites and enrolment

We anticipate the study enrolling patients through up to 10 large high volume CABG centres with interventional experience in all of the physiological techniques proposed in this study. We envisage enrolment would take place within 12 months.

10.3. Documentation

All documentation will be collected electronically using ICTU. The ICTU has a track record for running large multi-centre international (e.g. ASCOT study). Clinical, and physiological records will be saved to DVD and then to a central server within ICTU in accordance with GCP guidelines.

11. Publication policy

Publication and future studies committee

A publication committee, consisting of member of the steering committee and study principal investigators will meet to formulate a publication plan to disseminate the principal findings of the study, and the primary and secondary endpoints.

Future studies, and sub-studies will be actively encouraged, by investigators and other interested parties. These will be assessed via the formal application process, and the committee will decide on the applicability and suitability of the study request. Sub-study proposals which aim to look at subset analyses of the primary and secondary endpoints will be underpowered and in general discouraged.

12. References

4. Gillon R. Ethics needs principles--four can encompass the rest--and respect for autonomy should be "first among equals." *J Med Ethics.* 2003;29(5):307-312.
7. Lu ZL, Collaborative Group for China Coronary Secondary Prevention Using Xuezhikang. [China coronary secondary prevention study (Ccps)]. *Zhonghua Xin Xue Guan Bing Za Zhi.* 2005;33(2):109-115.

Appendix A Final Follow-up questionnaire

Have you had any of the following symptoms from atorvastatin over the past 6 months?			
Myalgias (muscle aches)	 Yes	 No	 Not Sure
Fatigue	 Yes	 No	 Not Sure
Mental fog (slow thinking or memory issues)	 Yes	 No	 Not Sure
Gastrointestinal upset	 Yes	 No	 Not Sure

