1.1. Study summary

Design

Patients will be randomized to receive either 30mg of atorvastatin or be presented with a choice of receiving either a “natural” statin (red yeast rice extract) or 30mg of atorvastatin.

In the intervention arm, a goal of either LDL-C reduction of at least 50% or an LDL-C < 100 mg/dl will be discussed on the initial visit. Goals will be re-assessed at 2 months, if goals are not met, patients will be given 30mg of atorvastatin.

Aims

To assess if introducing greater patient autonomy increases patient compliance with statin therapy.

Outcome measures

The primary endpoint will be 6-month compliance of statin therapy, after the initiation of atorvastatin.

Secondary endpoints will be rates of perceived side effects from statin use, including myalgias, fatigue, mental fog and GI upset.

Population

This will be a multi-center study of 300 pts, 150 in each arm.

Eligibility

Primary prevention (no history of CAD, MI, or stroke) patients with a moderate 10-year ASCVD risk who decline statin therapy.

Duration

Anticipated recruitment is 6 months. Follow-up will be performed at 6 months in the control arm and 2 and 8 months in the intervention arm, for a total study duration of 14 months.

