2.1. Background

Statin therapy is an integral tool in the primary and secondary prevention of ASCVD. Higher compliance with their statin therapy is associated with a lower risk of mortality in a step-wise manner (1). Despite this, rates of statin compliance are abysmally low. Prior studies suggest that less than 40% of primary prevention patients are compliant with their prescribed statin therapy. Individuals who have suffered a prior MI have an incremental improvement in compliance to around 60%. Younger individuals and women appear to have exceptionally low rates of compliance to statin therapy (2). Low rates of compliance remains a significant barrier to reducing the burden of ASCVD, with some suggesting efforts to increase compliance can have an oversized impact on reducing rates of ASCVD (3).

On the other hand, patients often prefer “natural” therapies over conventional medicine for a variety of reasons (6). Monacolin-K is a naturally occurring molecule in red yeast-rice extract, a commonly used health supplement. It is structurally identical to lovastatin and has been shown to reduce LDL-C levels and ASCVD events in randomized placebo controlled trials (7, 8).

Patient autonomy is a core bioethical principle affirming the right of the patient to determine the trajectory of their health care at times. This bioethical principle has been referred to as “first among equals”, implying that it is the most important bioethical principle (4). The role of autonomy in patient compliance is not entirely clear, but there is evidence that suggests that increased patient autonomy in the decision-making process can result in higher rates of long term compliance (5).

3. Study objectives

Primary Objective

The objective of this study is to determine if introducing autonomy in the decision-making process will increase statin compliance and reduce the rate of perceived side effects from statin use.

Rationale for the study

[figure not shown]
- 1) Statin use has been repeatedly shown to reduce the risk of ASCVD events
- 2) Patient compliance is a significant and often insurmountable barrier to statin therapy
- 3) Increased patient autonomy may be associated with greater rates of long-term compliance and warrants further investigation

Study hypotheses

Patients who perceive a higher degree of autonomy in the decision-making process are more likely to be compliant with statin therapy and less likely to perceive side effects from statin therapy.

4. Study design

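### The secondary endpoint covers side effects of statin use, but its only described form asks about atorvastatin in the last six months and cannot separate symptom-free takers from patients who never took it.

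*Protocol*

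**What the plan says.** Section 4.3 defines the secondary endpoint as "Rate of perceived side-effects from statin use, including muscle aches, fatigue, mental fog, and gastrointestinal upset". The summary in section 1.1 agrees: "Secondary endpoints will be rates of perceived side effects from statin use, including myalgias, fatigue, mental fog and GI upset". Neither limits the endpoint to atorvastatin.

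Section 4.2 gives one instrument for it, the four-item form in Appendix A, administered at the final follow-up. Its stem is "Have you had any of the following symptoms from atorvastatin over the past 6 months", and each symptom is answered Yes, No or Not Sure.

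The protocol treats red yeast rice as a statin. Section 1.1 labels it a natural statin, and section 2.1 says of its active molecule: "It is structurally identical to lovastatin". In the intervention arm it is used from baseline to the first return visit, whose purpose section 4.2 gives as follows: "Initial follow-up will take place in 2 months to assess the efficacy of their treatment". Patients not at the LDL goal then get atorvastatin and return six months later. Those at goal leave the analysis. Follow-up is at 6 months in control and at 2 and 8 months in intervention (sections 1.1 and 7).

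**The concern.** There are two gaps between the endpoint and the form.

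- **Coverage.** On the protocol's own description, the first two months on the supplement are statin use. A patient who had muscle aches on it and then moved to atorvastatin without further trouble answers 'No' truthfully, and the described forms record nothing.
- **Non-takers.** The trial enrols patients who decline statins (section 5.2), and the compliance score may be 0 (section 4.3). Some patients will probably never take the drug. They cannot truthfully report symptoms from it, and the form gives them no way to say so.

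Reducing perceived side effects is part of the objective and hypothesis in section 3, and the same hypothesis predicts different compliance by arm. A crude rate that moves with uptake would mix the two aims. Coding can be settled later in an analysis plan, but symptoms never asked about in months 0 to 2 cannot be recovered.

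**Working it through.** The protocol gives no rate or target difference for side effects, so there is no planned figure to reproduce. Its sample size of 138 concerns the primary endpoint and does not enter here.

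**Step 1: time covered by the form** (sections 1.1, 4.2 and 7, Appendix A)

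| Patient | Statin exposure by final visit | Window of the form | Not asked about |
|---|---|---|---|
| Control | atorvastatin, months 0–6 | months 0–6 | none |
| Intervention, supplement then switch | supplement 0–2, atorvastatin 2–8 | months 2–8 | supplement, months 0–2 |
| Intervention, at goal on supplement | leaves the analysis at month 2 | – | not in the comparison |

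For the switched patient the gap is 2/8 = 25% of exposure. Section 1.1 also lets intervention patients choose atorvastatin at the outset. If such a patient is seen at month 8, the first two months of atorvastatin fall outside the window.

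**Step 2: what the answers can show.** A 'No' can mean that the patient took the drug without symptoms, or never took it. Refill records help with the second case. Atorvastatin is prescribed as one supply plus five refills, and 1 + 5 = 6 matches the top of the 0–6 score. A score of 0 then appears to mean that nothing was dispensed. The protocol does not link this score to the form, and a dispensed supply is not proof that it was taken.

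**Step 3: effect on the crude rate.** Let r be the symptom rate among takers, equal in both arms, and t the share of takers in an arm. If every never-taker answers 'No':

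crude rate = r × t

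false difference (intervention minus control) = r × (t_I − t_C)

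All values of r and t below are assumptions.

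| r | t control | t intervention | Crude rate, control | Crude rate, intervention | False difference |
|---|---|---|---|---|---|
| 20% | 60% | 70% | 12% | 14% | +2 points |
| 20% | 70% | 60% | 14% | 12% | −2 points |
| 10% | 70% | 90% | 7% | 9% | +2 points |
| 20% | 70% | 90% | 14% | 18% | +4 points |
| 30% | 70% | 90% | 21% | 27% | +6 points |
| any | equal | equal | equal | equal | 0 |

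The 50% compliance in section 4.5 is an average compliance rate, not a share of takers, so it was not used for t.

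**Step 4: size against chance.** At a rate near 13% with 150 per arm, the standard error of the difference is √(2 × 0.13 × 0.87 / 150) = 0.039, or 3.9 points. A 2-point artefact is about half of that. Fewer than 150 intervention patients will be analysed if any reach goal on the supplement, so the true standard error would be somewhat larger.

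**The case against.** The restriction to atorvastatin may be deliberate. Controls and switched intervention patients are asked about the same drug over the same six months, and section 1.1 starts the primary endpoint at the initiation of atorvastatin. For that comparison the form is even-handed. This stands. A reader might infer that the form measures the two arms unequally throughout, but the documents do not support that for the shared atorvastatin period. If this narrower scope is meant, however, the endpoint wording does not say so, and the non-taker problem remains.

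A reader might also infer that the plan counts never-takers as symptom-free. It states no such rule. 'Not Sure' or a blank is possible, coding commonly belongs in an analysis plan, and refill records could identify patients who were never dispensed the drug. What remains is that the form itself cannot make the distinction.

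The case report form is also to be completed at the 2-month visit, and its content is not shown. One can say only that no described form asks about supplement symptoms, not that none will be recorded.

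The sizes rest on assumed rates, and the artefact can run either way. If the hypothesis of higher uptake under choice is right, it counts against the intervention, so no bias in its favour can be claimed.

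Finally, rewording the final form to cover every product taken would set eight months and two products against six months and one. That objection is sound, and the remedy below avoids such rewording.

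**Conclusion.** The point holds as a mismatch between endpoint and instrument. Two things follow from the text: supplement symptoms in months 0 to 2 are not asked about on any described form for patients who switch, and the form cannot tell a symptom-free taker from a never-taker. The first gap is 25% of exposure for those patients only; it does not apply to the whole arm.

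The distortion of the crude rate is a risk, conditional on never-takers answering 'No' and on uptake differing by arm. Under the assumptions shown it is 2 to 6 points in either direction, and zero with equal uptake. This is a secondary endpoint, but it is named in the trial's objective. The form should be corrected before use, because the missing answers cannot be collected afterwards.

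**What to change.** 1. Keep the common six-month atorvastatin window for the between-arm comparison, and reword the endpoint in sections 1.1 and 4.3 to name atorvastatin and that window.
2. Add a 'did not take atorvastatin' answer to Appendix A and cross-check it with the refill records.
3. Report the symptom rate in all allocated patients beside the share in each arm who took the drug. Give the rate among takers as descriptive only, since takers are selected after allocation. The first rate alone would still show 12% against 14% in the example; the uptake figures explain it.
4. Ask the same four questions about the supplement at the existing 2-month visit. Report them for the intervention arm separately, outside the between-arm comparison.

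The cost is a form edit and about a minute at a visit that already takes place. The drawback is that asking one arm about symptoms just before atorvastatin starts may prompt later reports in that arm. The outcome is perception, so this should be acknowledged in the protocol and in the report.
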